4 CEREBELLAR FUNCTIONS

HEAD TREMOR

- 0 none
- 1 mild
- 2 moderate
- 3 severe

TRUNCAL ATAXIA

- 0 none
- 1 signs only
- 2 mild: swaying with eyes closed
- 3 moderate: swaying with eyes open
- 4 severe: unable to sit without assistance

LIMB ATAXIA (TREMOR/DYSMETRIA AND RAPID ALTERNATING MOVEMENTS)

- 0 none
- 1 signs only
- 2 mild: tremor or clumsy movements easily seen, minor interference with function
- 3 moderate: tremor or clumsy movements interfere with function in all spheres
- 4 severe: most functions are very difficult

TANDEM (STRAIGHT LINE) WALKING

- 0 normal
- 1 impaired
- 2 not possible

GAIT ATAXIA

- 0 none
- 1 signs only
- 2 mild: abnormal balance only with tandem walking
- 3 moderate: abnormal balance with ordinary walking
- 4 severe: unable to walk more than a few steps unassisted or requires a walking aid or assistance by another person because of ataxia

ROMBERG TEST

- 0 normal
- 1 mild: mild instability with eyes closed
- 2 moderate: not stable with eyes closed
- 3 severe: not stable with eyes open

OTHER CEREBELLAR TESTS

- 0 normal
- 1 mild abnormality
- 2 moderate abnormality
- 3 severe abnormality

NOTE

The presence of severe gait ataxia alone (without severe truncal ataxia and severe ataxia in three or four limbs) results in a Cerebellar FS score of 3. If weakness on sensory deficits interfere with the testing of ataxia, score the patient's actual performance. To indicate the possible role of weakness make an "X" after the Cerebellar FS score.

FUNCTIONAL SYSTEM SCORE

- 0 normal
- 1 abnormal signs without disability
- 2 mild ataxia
- 3a moderate truncal ataxia
- 3b moderate limb ataxia
- 3c moderate or severe gait ataxia
- 4 severe truncal ataxia and severe ataxia in three or four limbs
- 5 unable to perform coordinated movements due to ataxia
- X pyramidal weakness (BMEC grade 3 or worse in limb strength) interferes with cerebellar testing

5 SENSORY FUNCTIONS

SUPERFICIAL SENSATION (LIGHT TOUCH AND PAIN)

- 0 normal
- 1 signs only; slightly diminished sensation (temperature, figure-writing) on formal testing of which patient is not aware
- 2 mild; patient is aware of impaired light touch or pain, but is able to discriminate sharp/dull
- 3 moderate; impaired discrimination of sharp/dull
- 4 marked; unable to discriminate between sharp/dull and/or unable to feel light touch
- 5 complete loss; anaesthesia

VIBRATION SENSE (AT THE MOST DISTAL JOINT)

- 0 normal
- 1 mild; graded tuning fork 5-7 of 8; alternatively, detects more than 10 seconds but less than the examiner
- 2 moderate; graded tuning fork 1-4 of 8; alternatively, detects between 2 and 10 sec.
- 3 marked; complete loss of vibration sense

POSITION SENSE

- 0 normal
- 1 mild; 1-2 incorrect responses, only distal joints affected
- 2 moderate; misses many movements of fingers or toes; proximal joints affected
- 3 marked; no perception of movement, ataxia

*** LHERMITTE'S SIGN**

Does not contribute to the Sensory FS score

- 0 negative
- 1 positive

*** PARAESTHESIAE (TINGLING)**

Does not contribute to the Sensory FS score

- 0 none
- 1 present

FUNCTIONAL SYSTEM SCORE

- 0 normal
- 1 mild vibration or figure-writing or temperature decrease only in one or two limbs
- 2a mild decrease in touch or pain or position sense and/or moderate decrease in vibration in one or two limbs
- 2b mild vibration or figure-writing or temperature decrease alone in three or four limbs
- 3a moderate decrease in touch or pain or position sense and/or essentially lost vibration in one or two limbs
- 3b mild decrease in touch or pain and/or moderate decrease in all proprioceptive tests in three or four limbs
- 4a marked decrease in touch or pain or loss of proprioception, alone or combined, in one or two limbs
- 4b moderate decrease in touch or pain and/or severe proprioceptive decrease in more than two limbs
- 5a loss (essentially) of sensation in one or two limbs
- 5b moderate decrease in touch or pain and/or loss of proprioception for most of the body below the head
- 6 sensation essentially lost below the head

6 BOWEL AND BLADDER FUNCTIONS

URINARY HESITANCY AND RETENTION

- 0 none
- 1 mild: no major impact on lifestyle
- 2 moderate: urinary retention; frequent urinary tract infections
- 3 severe: requires catheterisation
- 4 loss of function: overflow incontinence

URINARY URGENCY AND INCONTINENCE

- 0 none
- 1 mild: no major impact on lifestyle
- 2 moderate: rare incontinence occurring no more than once a week; must wear pads
- 3 severe: frequent incontinence occurring from several times a week to more than once a day; must wear urinal or pads
- 4 loss of function: loss of bladder control

BLADDER CATHETERISATION

- 0 none
- 1 intermittent self-catheterisation
- 2 constant catheterisation

BOWEL DYSFUNCTION

- 0 none
- 1 mild: no incontinence, no major impact on lifestyle, mild constipation
- 2 moderate: must wear pads or alter lifestyle to be near lavatory
- 3 severe: in need of enemas or manual measures to evacuate bowels
- 4 complete loss of function

*** SEXUAL DYSFUNCTION**

Male

- 0 none
- 1 mild: difficulty to maintain erection during intercourse, but achieves erection and still has intercourse
- 2 moderate: difficulty to achieve erection, decrease in libido, still has intercourse and reaches orgasm
- 3 severe: marked decrease in libido, inability to achieve full erection, intercourse with difficulty and hypogaesmia
- 4 loss of function

Female

- 0 none
- 1 mild: mild lack of lubrication, still sexually active and reaches orgasm
- 2 moderate: dyspareunia, hypogaesmia, decrease in sexual activity
- 3 severe: marked decrease in sexual activity, anorgasmia
- 4 loss of function

NOTE

When determining the EDSS step, the Bowel and Bladder FS score is converted to a lower score as follows:

Bowel and Bladder FS Score	Converted Bowel and Bladder FS Score
6	5
5	4
4	3
3	2
2	1

FUNCTIONAL SYSTEM SCORE

- 0 normal
- 1 mild urinary hesitancy, urgency and/or constipation
- 2 moderate urinary hesitancy and/or urgency and/or rare urinary incontinence and/or severe constipation
- 3 frequent urinary incontinence or intermittent self-catheterisation; needs enemas or manual measures to evacuate bowels
- 4 in need of almost constant catheterisation
- 5 loss of bladder or bowel function; external or indwelling catheter
- 6 loss of bowel and bladder function

7 CEREBRAL FUNCTIONS

DEPRESSION AND EUPHORIA

- 0 none
- 1 present: Patient complains of depression or is considered depressed or euphoric by the investigator or significant other.

DECREASE IN MENTATION

- 0 none
- 1 signs only: not apparent to patient and/or significant other
- 2 mild: Patient and/or significant other report mild changes in mentation. Examples include: impaired ability to follow a rapid course of association and in surveying complex matters; impaired judgement in certain demanding situations; capable of handling routine daily activities, but unable to tolerate additional stressors; intermittently symptomatic even to normal levels of stress; reduced performance; tendency toward negligence due to obliviousness or fatigue.
- 3 moderate: definite abnormalities on brief mental status testing, but still oriented to person, place and time
- 4 marked: not oriented in one or two spheres (person, place or time), marked effect on lifestyle
- 5 dementia, confusion and/or complete disorientation

*FATIGUE

- 0 none
- 1 mild: does not usually interfere with daily activities
- 2 moderate: interferes, but does not limit daily activities for more than 50 %
- 3 severe: significant limitation in daily activities (> 50 % reduction)

* Because fatigue is difficult to evaluate objectively, in some studies it does not contribute to the Cerebral FS score or EDSS step. Please adhere to the study's specific instructions.

NOTE

The presence of depression and/or euphoria alone results in a Cerebral FS score of 1a, but does not affect the EDSS step. However, a Cerebral FS score of 1b due to mild fatigue and/or signs only decrease in mentation contributes to the determination of the EDSS step.

FUNCTIONAL SYSTEM SCORE

- 0 normal
- 1a mood alteration (depression and/or euphoria) alone (does not affect EDSS step)
- 1b mild fatigue; signs only decrease in mentation
- 2 mild decrease in mentation: moderate or severe fatigue
- 3 moderate decrease in mentation
- 4 marked decrease in mentation
- 5 dementia

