Pulsed intravenous corticosteroid therapy, in the form of IVMP at a dose of 1 g monthly for 1 year, was chosen as an active comparator for the control arm. Corticosteroid pulses are widely used in clinical practice to improve energy and motor stamina in individuals with progressive MS. They have a favorable side effect profile. This treatment has not been rigorously tested in placebo-controlled, double-blind Phase 3 clinical trials. However, a randomized, controlled, single blind phase 2 clinical trial of regular pulses of IVMP administered to MS patients over 5 years showed beneficial effects including prevention or delay of whole brain atrophy and disability progression, and suppression of T1-weighted MRI lesion formation (Zivodinov et al., 2001)

The present study is designed to assess the safety and efficacy of ECP therapy compared with pulsed corticosteroids in patients with documented SPMS.

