8.1.2 EDSS

The EDSS form can be found in Appendix 2. The scores are calculated from the Functional System Score (FSS). EDSS and FSS will be determined by a single neurologist at baseline, and every 3 months through 2 years.

The EDSS is an ordinal scale with a 0.5-point increments ranging from 0-10.0. (increasing score indicates worsening) and based largely on ambulatory impairment in its middle range (EDSS 4.5-7.5 points).

0= normal neurological exam

10=death due to MS

Score 6 is still ambulatory with assistance

Score of 7 means patient must use a wheelchair.

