8. AMBULATION

Walking range as reported (without help or sticks)

meters	
in min	

Distance able to walk without rest or assistance

≥ 100 meters, but < 200 meters	
≥ 200 meters, but < 300 meters	
≥ 300 meters, but < 500 meters	
≥ 500 meters but not unrestricted	
Unrestricted	

Actual distance (obligatory up to 500 m if possible)

meters	
--------	--

Requires constant assistance to walk 100 meters

Unilateral assistance (in meters)	
Cane/crutch	
Other	
Bilateral assistance (in meters)	
Canes/crutches	
Other	
Assistance by another person (in meters)	

* = optional

* Because fatigue is difficult to evaluate objectively, in some studies it does not contribute to the Cerebral FS score or EDSS step. Please adhere to the study's specific instructions.

Standardised Neurological Examination and Assessment of Kurtzke's Functional Systems and Expanded Disability Status Scale
Slightly modified from J.F. Kurtzke, Neurology 1983;33,1444-52
©2007 Prof. L. Kappos, University Hospitals, Department of Neurology, CH-4031 Basel, Switzerland; Version 01/07

NEUROSTATUS SCORING

Definitions for a standardised, quantified neurological examination and assessment of Kurtzke's Functional Systems and Expanded Disability Status Scale in Multiple Sclerosis

Slightly modified from J.F. Kurtzke, Neurology 1983;33:1444-52
©2007 Prof. L. Kappos, University Hospitals, Department of Neurology,
CH-4031 Basel, Switzerland; Version 04/07

GENERAL GUIDELINES

To ensure unbiased EDSS assessment in controlled clinical trials, the EDSS rater should not inquire about the patients' condition except as necessary to perform the EDSS assessment. Patients must be observed to walk the required distance.

NEUROSTATUS (NS)

In the Neurostatus, "signs only" is noted when the examination reveals signs of which the patient is unaware.

FUNCTIONAL SYSTEMS (FS)

A score of 1 in a Functional System implies that the patient is not aware of the deficit and that the deficit or sign does not interfere with normal daily activities. However, this general rule does not apply to the Visual, Bowel/Bladder and Cerebral FS.

EXPANDED DISABILITY STATUS SCALE (EDSS)

The EDSS step should not be lower than the score of any individual FS, with the exception of the Visual and Bowel/Bladder FS. Signs or symptoms that are not due to multiple sclerosis will not be taken into consideration for assessments, but should be noted.

UE = upper extremities
LE = lower extremities
* = optional

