3 PYRAMIDAL FUNCTIONS

REFLEXES		Cutaneous Reflexes	
0	absent	0	normal
1	diminished	1	weak
2	normal	2	absent
3	exaggerated	* Palmonental Reflex	
4	nonsustained clonus	0	absent
5	(a few beats of clonus) sustained clonus	1	present
Plantar Response			
0	flexor		
1	neutral or equivocal		
2	extensor		

LIMB STRENGTH

The weakest muscle in each group defines the score for that muscle group. Use of functional tests, such as hopping on one foot and walking on heels/toes, are recommended in order to assess BMRC grades 3–5.

BMRC RATING SCALE

- 0 no muscle contraction detected
- 1 visible contraction without visible joint movement
- 2 visible movement only on the plane of gravity
- 3 active movement against gravity, but not against resistance
- 4 active movement against resistance, but not full strength
- 5 normal strength

FUNCTIONAL TESTS

- *Pronator Drift (upper extremities) Pronation and downward drift:
 - 0 none
 - 1 mild
 - 2 evident

*Position Test (lower extremities – ask patient to lift both legs together, with legs fully extended at the knee) Sinking:

- 0 none
- 1 mild
- 2 able to lift only one leg at a time (grade from the horizontal pos. at the hip joints...⁶)
- 3 unable to lift one leg at a time

*Walking on heels/toes

- 0 normal
- 1 impaired
- 2 not possible
- 3 hopping on one foot

LIMB SPASTICITY (AFTER RAPID FLEXION OF THE EXTREMITY)

- 0 none
- 1 mild: barely increased muscle tone
- 2 moderate: moderately increased muscle tone that can be overcome and full range of motion is possible
- 3 severe: severely increased muscle tone that is extremely difficult to overcome and full range of motion is not possible
- 4 contracted

GAIT SPASTICITY

- 0 none
- 1 barely perceptible
- 2 evident: minor interference with function
- 3 permanent shuffling: major interference with function

FUNCTIONAL SYSTEM SCORE

- 0 normal
- 1 abnormal signs without disability
- 2 minimal disability: patient complains of fatigue or reduced performance in strenuous motor tasks and/or BMRC grade 4 in one or two muscle groups
- 3a mild to moderate paraparesis or hemiparesis: usually BMRC grade 4 in more than two muscle groups or BMRC grade 3 in one or two muscle groups; movements against gravity are possible
- 3b severe monoparesis: BMRC grade 2 or less in one muscle group
- 4a marked paraparesis or hemiparesis: usually BMRC grade 2 in two limbs
- 4b moderate tetraparesis: BMRC grade 3 in three or more limbs
- 4c monoplegia: BMRC grade 0 or 1 in one limb

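### Appendix 2 counts fatigue toward the EDSS step unless the study instructs otherwise, and 8.1.2 gives no instruction: a subjective item enters an open-label endpoint, though its reach is limited

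*Combined protocol and SAP*

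**What the plan says.** Appendix 2 (13.2) reproduces the EDSS scoring rules. Under its heading 7, Cerebral Functions, fatigue is graded by how far it interferes with daily life. Mild fatigue gives Cerebral FS 1b, and the note there says that "a Cerebral FS score of 1b due to mild fatigue and/or signs only decrease in mentation contributes to the determination of the EDSS step". Grade 2 is defined as "mild decrease in mentation: moderate or severe fatigue". Fatigue is starred as optional, with this footnote: "Because fatigue is difficult to evaluate objectively, in some studies it does not contribute to the Cerebral FS score or EDSS step". The footnote ends: "Please adhere to the study's specific instructions".

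Fatigue also appears in a second place that the footnote does not cover. Under heading 3, Pyramidal Functions, grade 2 begins: "minimal disability: patient complains of fatigue or reduced performance in strenuous motor tasks".

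Section 8.1.2 says that the EDSS is calculated from the FS scores and that one neurologist rates every visit. It says nothing about fatigue or about blinding the rater. Nor do 3.2.1, 3.2.2, 10.2.1 or 10.2.2, where EDSS worsening is part of the primary endpoint and the EDSS score every 3 months is a secondary endpoint.

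Section 3.1 describes the study as open-label. On the control drug, section 1.1 says: "Corticosteroid pulses are widely used in clinical practice to improve energy and motor stamina in individuals with progressive MS".

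**The concern.** The appendix leaves the handling of fatigue to the study, and the study has not decided it. On the printed definitions fatigue counts. Its grade rests largely on what the patient reports about daily activities; that is an inference from how the grades are worded, and the footnote's remark on objectivity supports it. Patients know their treatment, the rater may know it, and only the control arm receives as study treatment a drug described as used for energy.

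The general guidelines in the same appendix set the opposite aim: "To ensure unbiased EDSS assessment in controlled clinical trials, the EDSS rater should not inquire about the patients' condition except as necessary". If fatigue changes differently in the two arms because of symptomatic relief or expectation, the EDSS can differ between arms with no difference in neurological worsening. That would touch a primary-endpoint component and, more directly, the secondary EDSS score.

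**Working it through.** **Inputs.** Eligible EDSS is 3 to 6.5 (4.1). Progression on EDSS is a rise of at least 1.0 from a baseline of 3 to 5.5, or at least 0.5 from a baseline of 6 or more (3.2.1, 10.2.1). Step definitions are in Appendix 2, heading 9. The most that fatigue alone can give is Cerebral FS 2.

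**Step 1: where FS grades cannot matter.** Heading 9 sets steps 5.5 to 8.0 by ambulation or wheelchair use alone. Fatigue therefore has no effect at 5.5 or above, which includes every patient to whom the 0.5-point threshold applies.

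**Step 2: mild fatigue (0 to 1b).** The definitions of 3.0 and 3.5 treat grades 0 and 1 alike. Coding the definitions for fully ambulatory patients, with the other six FS graded 0 to 4, a Cerebral change from 0 to 1 never moved an EDSS of 3.0 or more.

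**Step 3: moderate or severe fatigue (0 or 1 to 2).** Same coding:

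| Starting step | FS profiles that rise 0.5 | Rise of 1.0 |
|---|---|---|
| 3.0 | 9 of 13 | none |
| 3.5 | 11 of 16 | none |
| 4.0 | 6 of 43 | none |

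Example: one FS at 3 and the rest 0 goes from 3.0 to 3.5. The counts are of possible profiles, not of patients. Movement between 4.5 and 5.0 depends on walking range and rater judgement and was not modelled.

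**Step 4: can it tip the primary criterion?** Take three FS at grade 2, plus Cerebral FS 2 from fatigue at baseline. One FS then worsens from 2 to 3.

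| Handling of fatigue | Baseline | Follow-up | Rise | EDSS criterion |
|---|---|---|---|---|
| Counted, persists | 3.0 (four FS 2) | 4.0 (one FS 3, three FS 2) | 1.0 | met |
| Counted, relieved | 3.0 (four FS 2) | 3.5 (one FS 3, two FS 2) | 0.5 | not met |
| Never counted | 3.0 (three FS 2) | 3.5 (one FS 3, two FS 2) | 0.5 | not met |

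The underlying worsening is the same in each row. Across all one-grade worsenings of a single FS from a baseline of 3.0 with Cerebral FS 0, the criterion was met with or without new fatigue in 18 combinations, in neither case in 45, and only with fatigue in 15 (18 + 45 + 15 = 78). None of this last kind appeared at 3.5 or 4.0.

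**Step 5: the Pyramidal route.** If a fatigue complaint also moved Pyramidal FS from 1 to 2, four other FS at grade 2 (EDSS 3.0) would become six at grade 2 (EDSS 4.0). This is the only pattern found with a 1.0 rise on fatigue alone.

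**Step 6: entry.** Two FS at grade 2 is EDSS 2.5. Adding Cerebral FS 2 for fatigue makes three, which is 3.0, the entry minimum. The scoring rule is therefore needed at screening too.

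**Step 7: sensitivity of the design (illustration only).** The documents give no fatigue effect. With n per arm, power = Φ{[d√n − 1.645√(2p̄(1−p̄))] / √(p₁(1−p₁) + p₂(1−p₂))}, where d = p₂ − p₁ and p̄ is the mean of p₁ and p₂.

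- Plan's figure (10.4), 30% v 60%, n = 33: (1.723 − 1.157)/0.671 = 0.844, power 80.1%. The stated 66 patients are reproduced.
- Assumed control rate of 33% or 36% because fatigue relief hides progression: power 71.8% or 62.4%.
- Assumed spurious 3 or 6 points for ECP when both true rates are 30%: one-sided error 8.3% or 12.9% instead of 5%.

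Three to six points is 0.03 × 33 ≈ 1 to 0.06 × 33 ≈ 2 patients in one arm.

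**The case against.** The strongest reply is that the effect is small and bounded. Through the Cerebral FS it never reaches the 1-point threshold. It matters for the primary endpoint only in a patient at the lower EDSS levels who has another 0.5 rise, has not already failed on the walk or peg test, and has not dropped out (drop-outs count as non-responders under 10.2.1). At 4.0 to 5.0 walking range can override the FS grades. All of this stands and limits the size of the point.

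Second, section 3.1 places control-arm EDSS scoring in the week before the next infusion, with infusions every 4 weeks. This may well reduce a short-lived steroid effect. It does not address expectation.

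Third, a reader might infer that the protocol asserts a real energy benefit from steroids, and hence that worsening in the control arm will be hidden. The text does not support that. It describes usage, and section 1.1 adds that the treatment lacks rigorous placebo-controlled Phase 3 testing. No effect on fatigue is given.

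Fourth, the item is optional, and the footnote does not say what silence means, so a rater could leave fatigue out. That is fair, but the printed scoring note includes it, and an undecided rule in an open-label trial is not safer. Having a single rater limits inconsistency between raters; it does not remove knowledge of treatment.

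Fifth, either convention is legitimate. That also stands: excluding fatigue is a recommendation, while stating a rule is what the appendix itself calls for.

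**Conclusion.** The point holds in limited form. The printed rules count fatigue, the protocol gives no instruction, and the trial is open-label with no stated rater blinding, so a subjective item that treatment or expectation may affect enters the EDSS component of the primary endpoint and the secondary EDSS endpoint.

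Its size: nothing from mild fatigue at EDSS 3.0 or above, at most 0.5 from moderate or severe fatigue at about 3.0 to 5.0, and nothing at 5.5 or above. A reader might infer that fatigue alone can turn a patient into a progressor. Through the Cerebral FS it cannot; it can only complete a rise begun elsewhere. The single exception found needs the Pyramidal FS to move as well. The secondary EDSS score takes the 0.5 directly.

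The net direction is uncertain: relief on steroids would work against ECP, while expectation could favour it. How many of the 66 patients could be affected cannot be derived from the documents, so the power and error figures show sensitivity and are not estimates. The bounds rest on the Appendix 2 step definitions applied to fully ambulatory patients. The change is worth making because it closes a route for bias at almost no cost.

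**What to change.** Add to 8.1.2 and to the rater's instructions: *Fatigue is recorded but is left out when the Cerebral FS and the EDSS step are derived, at every visit including screening and baseline; a complaint of fatigue alone, without reduced motor performance or weakness on examination, does not raise the Pyramidal FS.*

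The second clause is needed because the Cerebral footnote does not reach Pyramidal grade 2. Covering screening and baseline keeps change scores and entry on the same scale.

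The cost is one sentence and a rater briefing, with no change to sample size, visits or treatment. The downside is that the EDSS becomes slightly less comparable with studies that count fatigue. The change does not resolve the wider question of whether the EDSS rater is blinded.
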